4.7 Other Analysis Sets

CCI

5 GENERAL METHODOLOGY AND CONVENTIONS

5.1 Hypotheses

Statistical inference will be made on the primary endpoint: percent change from baseline at Week 16 (Visit 11) in % liver fat assessed using MRI-PDFF. The null hypothesis is that there is no difference between PF-05221304 and placebo on the primary endpoint. The alternative hypothesis is that PF-05221304 is superior to placebo on the primary endpoint.

Mathematically, the null and alternative hypotheses are expressed as follows.

$$H_0 : \mu_i - \mu_0 = 0$$

vs.

$$H_a : \mu_i - \mu_0 < 0 ,$$

where μ_i is the mean percent change from baseline for PF-05221304 doses of 2 mg QD, 10 mg QD, 25 mg QD and 50 mg QD, and μ_0 is the mean percent change from baseline for placebo.

Statistical inferences for the primary endpoint will be done at a one-sided significance level of 10%. A dose is considered efficacious if the lower 90% lower confidence limit of $\mu_1 - \mu_0$ exceeds 0.

No Adjustment will be made for multiple comparisons.

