## 9.1. Sample Size Determination

The sample size for this study was based on interest to assess a dose-response for effect of PF-05221304 on percent change from baseline in liver fat (entire study population as well as separately in each sub-population in 1st tier stratification) and percent change from baseline in ALT in the 1st tier stratification sub-population of diagnosed/presumed NASH.

The proposed sample size for this study is approximately 360 subjects randomized (72 subjects per arm) to ensure at least 300 subjects (60 subjects per arm) complete the study.

The sample size of a minimum of 60 completers per arm, was calculated to yield  $\geq 80\%$  power to detect a placebo-adjusted, percent change from baseline of  $\geq 30\%$  in liver fat (in entire study population *and* in  $n=30$ /arm in each sub-population of the 1st tier stratification), using a 1-sided, t-test at level 10%. The calculation assumes that the standard deviation for liver fat is 7.8% (between-subject) and 6.2% (within-subject).

For the secondary endpoint of ALT in the 1st tier stratification sub-population of diagnosed/presumed NASH, the sample size of a minimum of 30 completers per arm was calculated to yield  $\geq 80\%$  power to detect a placebo-adjusted, percent change from baseline in ALT of  $\geq 35\%$ , using a 1-sided, t-test at level 10%. The calculation assumes that the standard deviation for the parameter of placebo-adjusted, percent change from baseline in ALT is 55% (between-subject).

Overall, via the planned interim analysis (refer to [Section 9.5](#)), if the observed standard deviation for the liver fat (MRI-PDF) and ALT data, based on unblinded review, is greater than the assumptions above, the sample size for this study *may* be adjusted upward, at sponsor discretion, to a maximum of 500 subjects randomized (ie, 100 subjects per arm).

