## 9.2. Efficacy Analysis

### 9.2.1. Analysis of the Primary Endpoint

The primary endpoint is placebo-adjusted, percent change from baseline in liver fat (via MRI-PDF) at Week 16, for the entire study population. A mixed model repeated measure (MMRM) analysis will be performed with treatment, time and treatment-by-time interaction as fixed effects, and subject as a random effect.

Descriptive summaries of the observed values and percent change from baseline in liver fat in each treatment group at each time point will be produced.

For statistical analyses, 80% confidence intervals will be produced for the least-square mean differences in each treatment group as compared to placebo. One sided p-values will be displayed for the comparison against placebo with no multiplicity adjustment made.

Dose-response modeling of the percent change from baseline in liver fat will be explored with total daily dose and time as a continuous variable to characterize and evaluate the dose-response relationship.

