5.2.1.2 Longitudinal Analysis

The over time effect of PF-05221304 on primary, secondary, and tertiary endpoints (see list in section 3) will be analyzed using the MMRM approach with randomized arm, time and randomized arm by-time interaction as fixed effects, subject as random effect using unstructured (UN) covariance structure. Baseline (in raw scale or log scale depending on the endpoint) will be included as covariate in the model.

Other covariance structures (eg Compound Symmetry (CS), Autoregressive(1) [AR(1)], Heterogeneous CS (CSH), and Heterogeneous AR(1) [ARH(1)]) will be considered if convergence in the previous model is not met.

The effect of PF-05221304 doses at all **post-randomization** visits will be estimated by the least-square (LS) means as well as LS mean differences against placebo respectively from the model described above.

For all analyses performed on log-transformed relative change from baseline (RCBL), the LS mean estimates and their corresponding confidence intervals (CIs) will be obtained for each randomized arm and week. Differences (and corresponding confidence intervals) between LS mean estimates will be obtained comparing randomized arms for each week. All LS means and LS mean differences (including CI's) will be back transformed to provide adjusted geometric LS means and ratios of adjusted geometric LS means. Then, percent change from baseline will be calculated as follows:

$$\text{Percent change} = 100 * (\text{RCBL} - 1)$$

where RCBL is either the adjusted geometric LS means estimate or the ratio of adjusted geometric means coming from the statistical model. The corresponding 80% CIs will be calculated as well.

For all analyses performed on raw scale, the LS means estimates and their corresponding confidence intervals (CIs) will be obtained for each randomized arm and week. Differences (and corresponding confidence intervals) between LS means will be obtained comparing randomized arms for each week.

Regardless if the data are analyzed in raw scale or after log-transformation, the inter- and intra-subject variability from the statistical model will be available and reported.

For % liver fat assessed by MRI-PDFP analyzed on log-scale, 80% confidence intervals will be presented for the LS geometric mean ratio.

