6.1.1 Primary Analysis on % Liver Fat assessed using MRI-PDF

Population: Entire Study Population

Endpoint: Relative change from baseline

Parameters: % Liver fat assessed with MRI-PDFP:

- Analysis time points: **all** applicable **post** Day 1/Visit 5 time points where **scheduled** assessment of specific continuous parameter is outlined in protocol
- Analysis population: FAS and PPAS (as sensitivity analysis).
- Analysis methodology: Log transformed relative change from baseline will be analyzed using MMRM model with log(baseline) as a covariate (specified in section 5.2.1.2).

Reporting results:

- Raw data and percent changes from baseline: Randomized subject, number of subject contributing to summary, sample size, mean, standard deviation, median, minimum, maximum, Q1 and Q3 at baseline and post-baseline visits will be presented for each randomized arm (see Appendix 2 for further detail).
- MMRM Outputs:
 - ✓ Adjusted geometric LS mean estimates with 80% confidence interval for each randomized arm along with the translation in percent change over time,
 - ✓ Ratio of adjusted geometric LS mean estimates for each active randomized arm against placebo and the corresponding 80% confidence interval along with the translation in percent difference over time.

Figures from MMRM outputs:

1. Line plot of percent change from baseline after back transformation of adjusted geometric LS means with 80% confidence interval over time (see Appendix 3.3),
2. Line plot of percent change from baseline placebo-adjusted after back transformation of adjusted geometric LS means ratios with 80% confidence interval over time (see Appendix 3.4),
3. Percent change from baseline after back transformation of adjusted geometric LS means with 80% confidence interval at Week 16 (see Appendix 3.5),
4. Percent change from baseline placebo-adjusted after back transformation of adjusted geometric LS means ratios with 80% confidence at Week 16 (see Appendix 3.6).

Note regarding the figures:

Instead of producing 4 independent figures, and in order to having a better understanding of the placebo effect, 1 figure containing side-by-side two panels presenting bullet 1 and 2 outputs (right panel for response over time and left panel for placebo adjusted response over time), and 1 figure with two panels presenting side-by-side bullet 3 and 4 outputs (right panel for response at Week 16 and left panel for placebo adjusted response at Week 16) should be produced.

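### The efficacy rule in SAP 5.1 uses the wrong confidence limit and the wrong direction, so it contradicts the alternative hypothesis stated just above it.

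*SAP*

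**What the plan says.** SAP 5.1 defines the means as percent change from baseline in liver fat at Week 16. The active-dose mean is μ_i, and μ_0 "is the mean percent change from baseline for placebo". The null is μ_i − μ_0 = 0 and the alternative is μ_i − μ_0 < 0. In words: "The alternative hypothesis is that PF-05221304 is superior to placebo on the primary endpoint". On the level, the section says "Statistical inferences for the primary endpoint will be done at a one-sided significance level of 10" percent.

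The decision sentence follows directly: "A dose is considered efficacious if the lower 90% lower confidence limit of" μ_1 − μ_0 exceeds 0.

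The other relevant places are:

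- SAP 3.5 defines change as observed minus baseline, so a fall in liver fat is negative. SAP 2 expects the drug to reduce liver fat.
- SAP 5.2.1.2, for the log-scale analysis: "Differences (and corresponding confidence intervals) between LS mean estimates will be obtained comparing randomized arms for each week". These are back-transformed to ratios and percent differences.
- SAP 6.1.1 lists as primary model output "Ratio of adjusted geometric LS mean estimates for each active randomized arm against placebo and the corresponding 80% confidence interval". It lists no p-value.
- Protocol 9.2.1 plans 80% intervals and adds "One sided p-values will be displayed for the comparison against placebo with no multiplicity adjustment made". It gives no criterion for calling a dose efficacious.

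**The concern.** For a contrast in which benefit is negative, a lower confidence limit above 0 is evidence of harm. The decision sentence and the alternative hypothesis therefore give opposite verdicts on the same data, within one section. An analyst who followed the sentence would fail the doses that work and could pass one that raises liver fat relative to placebo.

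The primary output list in SAP 6.1.1 offers confidence intervals and no p-value, so within the SAP a confidence limit is the natural thing to read the efficacy call from. If the conflict is noticed only after unblinding, the primary success criterion is settled with the results already known.

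**Working it through.** **1. Does the 90% level match the stated 10% one-sided test?** The normal quantile for one-sided 10% is 1.2816, the same as for a two-sided 80% interval. A one-sided 90% limit is therefore one end of the planned 80% interval, and the level is right. What remains to check is which end is used and in which direction.

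**2. What the written rule requires.** With SE the standard error of the difference, a lower limit above 0 means an observed difference greater than +1.2816 × SE. The rule that matches the alternative is an upper limit below 0, meaning an observed difference less than −1.2816 × SE.

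**3. Could another reading rescue the sentence?**

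- *Log difference or percent difference (SAP 5.2.1.2).* The null is still 0 and benefit is still negative, so the result is the same.
- *Geometric mean ratio (SAP 6.1.1).* The lower limit of a ratio is always above 0, so every dose would pass.
- *90% taken as a two-sided interval.* The threshold moves to +1.645 × SE, still in the harmful direction.
- *Contrast reversed to placebo minus active.* No readable text does this.

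**4. Probability of being called efficacious.** The inputs are n = 60 completers per arm (Protocol 9.1), SE = SD × √(2/60) and true difference d.

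- Written rule: 1 − Φ(1.2816 − d/SE)
- Matching rule: Φ(−1.2816 − d/SE)

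Protocol 9.1 gives SDs for liver fat ("The calculation assumes that the standard deviation for liver fat is 7.8% (between-subject) and 6.2% (within-subject") but does not clearly give an SD for percent change. SDs of 20, 30 and 40 percentage points are therefore assumed, giving SE 3.65, 5.48 and 7.30.

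| True difference (points) | Rule | SD 20 | SD 30 | SD 40 |
|---|---|---|---|---|
| −30 | written | <0.0001 | <0.0001 | <0.0001 |
| −30 | matching | 1.000 | 1.000 | 0.998 |
| −10 | written | 0.00003 | 0.0009 | 0.0040 |
| −10 | matching | 0.927 | 0.707 | 0.535 |
| 0 | either | 0.10 | 0.10 | 0.10 |
| +10 | written | 0.927 | 0.707 | 0.535 |

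Using a noncentral t with 118 degrees of freedom changes these by at most about 0.002.

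**5. With the Protocol's own SDs.** Suppose both are read as percent-change points and combined: √(7.8² + 6.2²) = 9.96, so SE = 1.82. At d = −10 the written rule passes with probability below 0.0001 and the matching rule with probability above 0.9999.

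**6. On the log scale that the model uses.** For a true ratio of 0.70, d = ln 0.70 = −0.357. With assumed log SDs of 0.30, 0.45 and 0.60, the written rule passes with probability below 0.0001 in each case. The matching rule passes with 1.000, 0.999 and 0.976.

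**7. One worked result.** Take an observed ratio of 0.70 and log SD 0.45, so SE = 0.45 × √(2/60) = 0.0822. The 80% interval is −0.357 ± 1.2816 × 0.0822 = (−0.462, −0.251), or −37.0% to −22.2% as a percent difference. The lower limit, −0.462, is not above 0, so the written rule fails this dose. The upper limit, −0.251, is below 0, so the matching rule passes it.

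**The case against.** The strongest reply is that this is a drafting slip that could hardly be applied unnoticed. The alternative hypothesis and the one-sided 10% level together already define a complete and correct test. Protocol 9.2.1 plans one-sided p-values, and Protocol 9.1 sizes the trial on a one-sided 10% t-test. The sentence repeats the word lower and writes μ_1 where the hypotheses use μ_i, which also points to careless editing. Little depends on the label: the primary objective is dose-response, there is no multiplicity adjustment, and the interim work in SAP 7.2 uses liver-fat data only up to Day 1.

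Most of this stands. The correct test can be inferred, the intent is not in doubt, and the probabilities above measure what literal use would do, not a likely loss. Two qualifications also stand. The rule is met by an *observed* result significantly worse than placebo; a dose with no true effect meets it by chance 10% of the time. And a working dose is failed almost always rather than always, with up to 0.004 passing at −10 points and SD 40.

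A further point concerns the repair: SAP 5.1 writes its hypotheses in mean percent change, while the model estimates a log difference that is back-transformed to a ratio. A corrected rule should name its scale.

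None of this makes the sentence right. An analyst should not have to override a prespecified decision rule by inferring its intent from the lines around it.

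**Conclusion.** The concern holds. The decision sentence in SAP 5.1 contradicts the alternative hypothesis in the same section: both the limit and the inequality are reversed, while the 90% level and, on the difference scales, the zero cut-off are right. Followed literally, it almost never passes a dose that works and often passes one that does worse than placebo. The sizes above rest on assumed SDs; the direction of the error does not depend on them. The significance level, sample size, estimates and reported 80% intervals are untouched, so this is a correction of text. It matters because no other sentence in the readable text states when a dose is considered efficacious on the primary endpoint.

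**What to change.** Replace the decision sentence in SAP 5.1 with wording such as:

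> Dose i is considered efficacious if the upper one-sided 90% confidence limit (the upper limit of the two-sided 80% confidence interval) of the Week 16 placebo-adjusted effect is below 0 on the log-difference or percent-difference scale; equivalently, if the upper limit of the geometric mean ratio versus placebo is below 1. The rule applies to each of the four doses.

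A short clause in the same edit should say that the hypotheses are tested on the log relative-change scale of SAP 5.2.1.2, so that the rule and the hypotheses refer to the same parameter. The change costs no patients and no extra analysis, because the 80% intervals are already planned. It is best made before unblinding.

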5.2 General Methods

5.2.1 Analyses for Continuous Data

5.2.1.1 Descriptive Statistics

Each endpoint will be summarized accordingly to Appendix 2.

5.2.1.2 Longitudinal Analysis

The over time effect of PF-05221304 on primary, secondary, and tertiary endpoints (see list in section 3) will be analyzed using the MMRM approach with randomized arm, time and randomized arm by-time interaction as fixed effects, subject as random effect using unstructured (UN) covariance structure. Baseline (in raw scale or log scale depending on the endpoint) will be included as covariate in the model.

Other covariance structures (eg Compound Symmetry (CS), Autoregressive(1) [AR(1)], Heterogeneous CS (CSH), and Heterogeneous AR(1) [ARH(1)]) will be considered if convergence in the previous model is not met.

The effect of PF-05221304 doses at all **post-randomization** visits will be estimated by the least-square (LS) means as well as LS mean differences against placebo respectively from the model described above.

For all analyses performed on log-transformed relative change from baseline (RCBL), the LS mean estimates and their corresponding confidence intervals (CIs) will be obtained for each randomized arm and week. Differences (and corresponding confidence intervals) between LS mean estimates will be obtained comparing randomized arms for each week. All LS means and LS mean differences (including CI's) will be back transformed to provide adjusted geometric LS means and ratios of adjusted geometric LS means. Then, percent change from baseline will be calculated as follows:

$$\text{Percent change} = 100 * (\text{RCBL} - 1)$$

where RCBL is either the adjusted geometric LS means estimate or the ratio of adjusted geometric means coming from the statistical model. The corresponding 80% CIs will be calculated as well.

For all analyses performed on raw scale, the LS means estimates and their corresponding confidence intervals (CIs) will be obtained for each randomized arm and week. Differences (and corresponding confidence intervals) between LS means will be obtained comparing randomized arms for each week.

Regardless if the data are analyzed in raw scale or after log-transformation, the inter- and intra-subject variability from the statistical model will be available and reported.

For % liver fat assessed by MRI-PDFP analyzed on log-scale, 80% confidence intervals will be presented for the LS geometric mean ratio.

For endpoints which are on raw scale, 80% confidence intervals will be presented for the LS mean differences along with the corresponding two-sided *p*-values when changes from baseline is the primary parameter.

For other endpoints that, similar to % liver fat assessed by MRI-PDF, are log-transformed, 80% confidence intervals will be presented for the LS geometric mean ratio.

The LS means and corresponding standard errors will be plotted over time by randomized arms.

If, for any endpoint, there are major deviations from statistical assumptions underlying the MMRM model then alternative transformations or non-parametric analyses may be presented. Justification for any alternative to the planned analysis will be given in the study report.

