9 APPENDICES

Appendix 1. SUMMARY OF EFFICACY ANALYSES

Endpoint	Analysis Set	Statistical Method	Model/ Covariates/ Strata	Missing Data	Interpretation
Percent change from Baseline in % Liver Fat assessed by MRI-PDFD Over Time	FAS and PPAS	MMRM on log-transformed relative change	Treatment, time and treatment-by-week interaction as fixed effects, subject as random effect with log(baseline) as covariate.	No Imputation	Primary Analysis
Percent Change from Baseline in % Liver Fat assessed by MRI-PDFD at Week 16	FAS and PPAS	ANCOVA on log-transformed relative change	Treatment, Weight and treatment-by-Weight interaction as fixed effects, subject as random effect with log(baseline) as additional covariate.	No Imputation	Sensitivity analysis with two covariates on primary endpoint.
Percent Change from Baseline in % Liver Fat assessed by MRI-PDFD at Week 16	FAS and PPAS	ANCOVA on log-transformed relative change	Treatment, concomitant drug and treatment-by-concomitant drug interaction as fixed effects, subject as random effect with log(baseline) as additional covariate.	No Imputation	Sensitivity analysis with two covariates on primary endpoint.
Percent Change from Baseline in % Liver Fat assessed by MRI-PDFD at Week 16	FAS	Dose-Response model	See section 5.2.1.3	No Imputation	Supportive analysis on primary endpoint
Percent change from Baseline in ALT Over Time	FAS	MMRM on log-transformed relative change	Treatment, time and treatment-by-week interaction as fixed effects, subject as random effect with log(baseline) as covariate.	No Imputation	Secondary analysis

Endpoint	Analysis Set	Statistical Method	Model/ Covariates/ Strata	Missing Data	Interpretation
Percent Change from Baseline in ALT at Week 16	FAS	Dose-Response model	See section 5.2.1.3	No Imputation	Supportive Analysis on secondary endpoint
Tertiary endpoints: Change from Baseline over time	FAS	MMRM on change from baseline	Treatment, time and treatment-by-week interaction as fixed effects, subject as random effect and baseline as covariate	No Imputation	Tertiary analysis
Tertiary endpoints: Percent change from Baseline over time other than % Liver Fat using MRI-PDF	FAS	MMRM on log-transformed relative change	Treatment, time and treatment-by-week interaction as fixed effects, subject as random effect and log(baseline) as covariate.	No Imputation	Tertiary Analysis

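### The SAP's MMRM adds a random subject effect to an unstructured covariance, so the inter-/intra-subject split it promises is not identified; Week 16 inference is at risk only if the fit fails and falls back to CS or AR(1)

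*SAP*

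**What the plan says.** SAP 5.2.1.2 covers the primary, secondary and tertiary longitudinal analyses. It fits arm, time, arm-by-time and baseline, with "subject as random effect using unstructured (UN) covariance structure". Protocol 9.2.1 names only a random subject effect and no covariance structure.

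The SAP gives CS, AR(1), heterogeneous CS (CSH) and heterogeneous AR(1) (ARH(1)) as examples of alternatives that "will be considered if convergence in the previous model is not met". It states no order, selection rule, degrees-of-freedom method or robust standard error for the MMRM. A sandwich estimator appears only in 5.2.2, for recurrent events.

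The same section says that "the inter- and intra-subject variability from the statistical model will be available and reported".

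In SAP Appendix 1, the two Week 16 liver-fat ANCOVA rows also carry "subject as random effect with log(baseline) as additional covariate". Section 5.2.1.4, which describes those ANCOVAs, has no subject term.

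For liver fat, SAP 5.1 sets a one-sided 10% level with no multiplicity adjustment, and 5.2.1.2 says that "80% confidence intervals will be presented for the LS geometric mean ratio".

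**The concern.** An unstructured matrix already describes every variance and covariance among a subject's visits. A random subject effect adds a constant to every element of that matrix, and the unstructured part can absorb any such constant. Two consequences follow.

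First, the subject variance has no unique estimate, so the inter-/intra-subject output promised in 5.2.1.2 would depend on the software and its starting values. The same holds for the Appendix 1 ANCOVAs, where each subject contributes one observation and subject variance cannot be told apart from residual variance.

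Second, software may fix the redundant term at zero, report a singular fit or fail to converge. Failure opens the fallback list. CS and AR(1) force one variance on all visits, and AR(1) and ARH(1) treat unequally spaced visits as equally spaced. If the Week 16 variance differs from the average, a model-based Week 16 standard error under CS or AR(1) is wrong. That standard error sets the 80% interval and the 10% test for each dose.

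**Working it through.** **Inputs from the documents.** One-sided level 10% (SAP 5.1); 80% intervals (SAP 5.2.1.2); MRI at Weeks 4, 12 and 16, with gaps of 8 and 4 weeks (SAP Appendix 2.2.1); ALT at Weeks 2, 4, 6, 8, 12 and 16, plus follow-up (SAP Appendix 2.2.4); five arms of 72 randomized for 60 completers (Protocol 9.1).

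**Not in the documents.** The SD of log relative change by visit and the correlation between visits. Both are assumed below: correlation constant at 0.7, or 0.95 per week of separation.

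**Step 1: the plan's own figure.** The one-sided 10% critical value is z(0.90) = 1.2816, which is also the multiplier of a two-sided 80% interval. The two statements agree.

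**Step 2: identification.** With m visits, an unstructured matrix R has m(m+1)/2 parameters. Adding a subject variance s² gives V = s²J + R, where J is all ones; V still has m(m+1)/2 distinct elements.

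- MRI, m = 3: 6 + 1 = 7 parameters for 6 elements.
- ALT, m = 6: 21 + 1 = 22 for 21.

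Every s² from 0 to 1/(1′V⁻¹1) reproduces the same V. With assumed SDs of 0.25/0.35/0.40 and correlation 0.7, that means any value from 0 to 0.0615. In one simulated batch with these SDs, the fits started at s² = 0.0162 and finished between 0.0115 and 0.0180, although nothing in the data favours those values.

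**Step 3: effect on Week 16 inference if the fit converges.** Estimates and standard errors depend on V, which is identified. In simulation (five arms of 72, outcome-dependent monotone dropout), adding a random intercept to the unstructured model changed the Week 16 differences by at most about 1e-8 and their standard errors by at most 3e-7 in relative terms.

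**Step 4: effect of a fallback.** With complete data, the CS variance is the mean of the visit variances, so

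level = 1 − Φ(1.2816 × √(mean variance / Week 16 variance)), and coverage = 1 − 2 × level.

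For SDs 0.25/0.35/0.40: mean variance = (0.0625 + 0.1225 + 0.1600)/3 = 0.1150; √(0.1150/0.1600) = 0.848, so the standard error is 15% too small; level = 1 − Φ(1.087) = 13.9%; coverage = 72.3%.

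For the other structures, V is the member of the family that minimises log|V| + tr(V⁻¹Σ), where Σ is the assumed covariance, and its Week 16 variance replaces the mean variance in the formula. One-sided level for liver fat:

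| Assumed SDs, Weeks 4/12/16 | CS | AR(1) | CSH | ARH(1) |
|---|---|---|---|---|
| 0.40/0.40/0.40 | 10.0% | 10.0% | 10.0–10.1% | 10.0–10.8% |
| 0.35/0.40/0.42 | 11.6% | 11.7–11.8% | 10.0–10.1% | 10.0–10.8% |
| 0.25/0.35/0.40 | 13.9% | 14.0% | 10.0–10.1% | 10.0–10.8% |
| 0.20/0.30/0.40 | 16.0% | 15.8% | 10.0–10.1% | 10.0–10.8% |
| 0.45/0.40/0.35 | 7.0% | 7.0% | 10.0–10.1% | 10.0–10.8% |

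Ranges cover the two correlation patterns.

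**Step 5: simulation with dropout.** REML, 1,400 trials per scenario, Monte Carlo error about ±1 point. At 0.25/0.35/0.40 the levels were: unstructured 10.8%, CSH 11.1%, ARH(1) 11.6%, AR(1) 15.4%, CS 15.7%.

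**Step 6: ALT.** With six visits and SDs rising from 0.25 to 0.42, the levels were CS 15.3%, AR(1) 15.0–15.1%, CSH 8.3–10.0% and ARH(1) 8.0–10.0%.

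**The case against.** The strongest reply is that the phrase is loose shorthand for an unstructured within-subject covariance. On that reading nothing in the MMRM is over-parameterised. With three MRI visits and 300–360 subjects, a plain unstructured fit is unlikely to fail, and it ran without trouble in simulation. This is plausible, but the SAP does not say it, and a plain unstructured model still yields no inter-/intra-subject split, so the promised output would still lack a source.

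A reader might infer that the redundant term by itself makes the Week 16 intervals or the 10% level wrong. It does not, because the total covariance is identified (step 3).

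A reader might also infer that every listed fallback assumes equal variances or equal spacing. CSH assumes neither: it allows a variance per visit and a constant correlation. ARH(1) allows unequal variances, and for MRI its spacing error costs about one point or less.

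The Appendix 1 wording can fairly be called a slip in a summary table, in rows labelled as sensitivity analyses. With one observation per subject the fixed-effect inference is unaffected. It still contradicts 5.2.1.4.

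Three further remedies are tempting but not supported:

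- A spatial-power structure respects the spacing but keeps one variance for all visits. It gives 14.2–14.3% for SDs 0.25/0.35/0.40 and 16.2% for 0.20/0.30/0.40.
- Heterogeneous Toeplitz uses one lag-1 correlation for both the 8- and 4-week gaps.
- A covariance matrix per arm raises the liver-fat parameters from 6 to 30. A common matrix is the usual default, and the documents give no arm SDs to argue against it.

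**Conclusion.** The specification needs correcting, but the primary inference is not shown to be wrong. As worded, the model is over-parameterised by one term, the inter-/intra-subject output promised from it cannot be delivered, and Appendix 1 contradicts 5.2.1.4.

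The threat to the Week 16 level is conditional on two events: the fit fails, and the unordered list then leads to CS or AR(1) with model-based standard errors. In that case the one-sided level would be about 14–16% for the two steeper rising patterns, nearer 12% for a mild rise, 10% for equal SDs and 7% for falling SDs. Coverage of the 80% interval would run from about 68% to 86%. All of these rest on assumed SDs and correlations. If the fallback were CSH or ARH(1), the liver-fat level would stay at 10.0–10.8% in large samples.

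**What to change.** 1. In SAP 5.2.1.2 and the Appendix 1 MMRM rows, delete the separate random subject effect, state that the unstructured matrix is the within-subject residual covariance, and name Kenward-Roger degrees of freedom.
2. In Appendix 1, delete the random subject effect from the Week 16 ANCOVA rows, in line with 5.2.1.4.
3. Fix the fallback order: CSH, then ARH(1), with CS or AR(1) only as a last resort. Report empirical (sandwich) standard errors for any fallback, and name the degrees-of-freedom method used with them.
4. Take inter- and intra-subject variability from a separate random-intercept model and say so. SAP 7.2 already uses a model of this kind for the MRI data at the interim.

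The cost is SAP wording, a few program options and slightly more programming. No data collection or sample size changes.
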